Performance effects resulting from the messages provided to athletes shouldn't be ignored, and this is referred to as placebo (has a perceived positive effect) or nocebo (has a perceived negative effect (Horvath, 2021). The concept of performance decline after negatively-perceived stimulus has a less robust presence in the literature than placebo effects, though this is evolving. Numerous recent studies have now documented the significant detriments to physical performance when subjects are exposed to negative or potentially threatening information (Cook, 2012; Corsi, 2019; Emadi Andani, 2015; Horcajo, 2019; Jackson, 2005; Pollo, 2012; Zech, 2019).

To our knowledge, there are no longitudinal studies evaluating the risk of injury from deadlifting with a flexed lumbar spine resulting in no clear evidence that a flexed spine is a risk factor for injury. However, it is well documented that information related to potential threat (nocebo) can adversely affect physical performance. Our research aim is to determine if cautionary information about the risk of spine injury harms performance on a maximum strength test compared to a message of spine resiliency. The cautionary education is similar to standard information provided to many servicemembers before the start of an ACFT or a maximum deadlift.

9.3

Objectives/Specific Aims/Research Questions:

Describe the purpose and objective(s) of the study, specific aims, and/or research questions /hypotheses

1. Determine if general self-efficacy is a predictor of injury during Cadet Basic Training(CBT) by performing a Kaplan-Meier Survival Curve of a single self-efficacy assessment (Cadet General Self-Efficacy Assessment) and injury occurrence using the Defense Medical Surveillance System (DMSS), Cadet Illness and Injury Tracking System (CIITS), Armed Forces Health Longitudinal Technology Application (AHLTA) and a follow-up self-reported injury assessment.

1. Independent Variable: Cadet General Self-Efficacy score

2. Dependent Variables: Injury report according to CIITS, AHLTA, DMSS, sick call report or self-reported

2. Determine if task-specific self-efficacy is a predictor of injury during specific CBT events by performing a Kaplan-Meier Survival Curve, a single assessment of cadet task-specific self-efficacy and injury occurrence using DMSS, CIITS, AHLTA and a follow-up self-reported injury assessment.

1. Independent Variable: Cadet Task-Specific Self-Efficacy score

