Researchers inside and outside of the military have also found that self-efficacy predicts both performance and is negatively correlated with MSKI (Gruber et al., 2009; Samuels et al., 2010). In a study on Navy SEAL training resilience, researchers found that successful graduation was related to physiological markers of resilience (Ledford et al., 2020). However, few studies have investigated the combined effects of physical, behavioral and psychological factors on predicting MSKIs.

Cadet basic training (CBT) at the United States Military Academy (USMA) is a 7-week initial-entry training event that physically and psychologically prepares cadets to become officers. It includes similar training events and physical demands as other initial-entry military courses such as a 12-mile foot march with 35 lbs., physical training including running multiple days per week, weapons familiarization, and basic tactical training. The injury risk factors for cadets attending CBT are similar to trainees attending U.S. Army Basic Combat Training and regular military training even though injury incidence is lower (Hearn et al., 2021). Identifying self-efficacy as an injury risk factor is the first step to designing and implementing injury prevention measures. The purpose of this study is to investigate relationships between performance, MSKI and self-efficacy alone and in combination with other MSKI risk factors in USMA cadets participating in CBT.

There is currently an emphasis in Army Doctrine (FM 7-22) on form/technique for events on the ACFT, especially the maximum deadlift (MDL) and the prevention of lower back injuries. The rationale behind this is due to the perception that breakdowns in form during the deadlift lead to injuries, however, the research does not support this. Specifically, the research is unclear regarding the position of the spine while deadlifting- neutral vs flexed. Our results could impact future DoD publications regarding technique on the MDL and de-emphasize the role of a rounded spine as a safety concern.

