The researchers hypothesize that self-efficacy (general and task-specific) will be positively correlated with successful completion and performance and negatively correlated with MSKI risk during CBT. The researchers will also explore the relationship between self-efficacy and other known injury risk factors. Furthermore, we hypothesize that such beliefs about the vulnerability of the spine to injury might contribute to future disabling beliefs about back pain. This research marks an important step in investigating the role of beliefs about the back and readiness.

10.0

Study Procedures, Data Management, and Privacy

10.1 Study Procedures:

Describe step-by-step how the study will be conducted from beginning to end

Phase I: Consent and Self-Efficacy Assessment

All new cadets are eligible to participate in this study and will receive verbal and written study description during the first or second week of cadet basic training. Immediately after consenting to participate, they will complete the study demographic data information and the Cadet Basic Training Projective Performance

Invent01y, which assesses self-efficacy measured prospectively via questionnaire on a 10-point Likert scale from 1 (no confidence) to 10 (fully confident) for overall performance during cadet basic training, marksmanship/live fire training, mock marching 12 miles, land navigation, swimming, and the Army Combat Fitness Test. It will also assess for any recent injuries and whether the injury is currently hindering them.

Phase 2: Injury Surveillance During Cadet Basic Training

These researchers will monitor the Cadet Injury and Illness Tracking System (CIITS), Armed Forces Health Longitudinal Technology Application (AHLTA) and the Defense Medical Surveillance System (DMSS) up to weekly to track injuries for the duration and for up to 9 weeks afterwards. They will classify injuries as by diagnosis, region, and impact on training ("not injured" (1), "injured-not limited" (2), "injured-modified training" (3) and "injured-limited" (4)). Cadets will initially be defaulted as "not injured" (1). They will also complete the Single Assessment Numeric Evaluation (SANE), rating their current ability level on a scale of 0-100% with regards to their injury.

Phase 3: Maximum Deadlift and Low Back Pain Education

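### The injury analyses (Objectives 1 and 2) set no time origin, at-risk set or end date, so nothing keeps injuries that precede the week 1-2 self-efficacy score from counting as predicted by it

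*Combined protocol and SAP*

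**What the plan says.** - **When the score is taken.** Under 10.1, Phase I, cadets "will receive verbal and written study description during the first or second week of cadet basic training". The forms follow at once: "Immediately after consenting to participate, they will complete the study demographic data information", together with the self-efficacy inventory. Sections 13.1 and 13.4 describe one mass session, with consent taken from everyone together. Section 9.6 says CBT "is a 7-week initial-entry training event".
- **Baseline injury.** Of the same form, 10.1 says: "It will also assess for any recent injuries and whether the injury is currently hindering them". Section 10.2 sets the look-back at one year. Section 12.6 lists no exclusion criteria.
- **Surveillance.** Under 10.1, Phase 2, the record systems are checked "up to weekly to track injuries for the duration and for up to 9 weeks afterwards". On starting status: "Cadets will initially be defaulted as" 'not injured', code 1 of a four-level scale of training impact.
- **Outcome and method.** Sections 9.3 and 11.6 (items 1-2) plan Kaplan-Meier analyses of injury during CBT or its events. The outcome is an injury found in the records or self-reported. Phase 5 adds a questionnaire after CBT. Section 10.2 lists its injury variables as presence, region and limiting classification, with no date.
- **Not stated.** Neither 11.1 nor 11.6 gives a time origin, an at-risk set, a rule for injuries already present, or an end of follow-up for the injury analyses. Neither gives the baseline injury answer a role in them.

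**The concern.** A predictor has to be measured before the event it predicts. Here the course is already under way when the score is taken, and two kinds of injury could enter as events without meeting that condition:

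- **(a)** an injury in CBT before the questionnaire;
- **(b)** an injury present at the questionnaire that appears in the records, or is reported, later.

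In both, the injury may have lowered the confidence rating, so the association could run from injury to score. That is the direction hypothesised in 9.6 (higher self-efficacy, fewer injuries). Section 9.6 treats identifying self-efficacy as a risk factor as the first step towards prevention measures, and 14.4 says training in self-efficacy might follow if the correlation is found. An artefact of timing would be a poor basis for either.

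There is also a mismatch at the other end. The objectives concern CBT, while surveillance continues for up to 9 weeks after it, and the plan does not say which window the survival analysis uses.

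**Working it through.** The plan gives no event count, injury rate or power for Objectives 1 and 2. Its only computed sample size (969, in 11.5) is for the deadlift comparison, so there is no figure of the plan's own to reproduce here.

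**Step 1: share of time before the score.** Inputs from the documents: CBT T = 7 weeks; questionnaire at time w during week 1 or 2; up to 9 further weeks of surveillance. Share = w/T.

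- Session on the first day: 0/7 = 0%.
- End of week 1: 1/7 = 14%.
- End of week 2: 2/7 = 29%.
- If the window is 7 + 9 = 16 weeks: 0% to 2/16 = 12.5%.
- Share of the 16 weeks that falls after CBT: 9/16 = 56%.

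**Step 2: share of first injuries before the score.** Assumption: 25% of cadets injured over 7 weeks at a constant rate, so λ = -ln(0.75)/7 = 0.0411 per week. Share = (1 - exp(-λw))/0.25.

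- w = 1: 0.0403/0.25 = 16%.
- w = 2: 0.0789/0.25 = 32%.

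**Step 3: what this could do to the test.** Simulation with no true effect of self-efficacy: 1,000 cadets, 2,000 runs per scenario, and a log-rank test at 5% on a median split (the plan gives no cut-point). The score is lowered by an assumed amount in cadets already injured. Injury risk, score shift and prevalence are all assumptions. The 16-week column extends the same constant rate. 'Hindered' means that 5% arrive with a hindering injury and half of them are seen for it during CBT.

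| CBT risk | Questionnaire | Score shift | Hindered | False positives, 7 weeks | False positives, 16 weeks |
|---|---|---|---|---|---|
| 25% | mid-week 1 | 0.5 SD | none | 7-8% | 7-8% |
| 25% | end week 1 | 0.5 SD | none | 16% | 10% |
| 25% | end week 1 | 0.5 SD | 5% | 28% | not computed |
| 25% | end week 2 | 0.25 SD | none | 17% | 10% |
| 25% | end week 2 | 0.25 SD | 5% | 20% | not computed |
| 25% | end week 2 | 0.5 SD | none | 47% | 27% |
| 25% | end week 2 | 0.5 SD | 5% | 59% | not computed |
| 10% | end week 2 | 0.5 SD | none | 20% | 12% |

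Independent repeats of the 7-week cells at 25% risk agreed within about three percentage points. For a 0.5 SD shift at the end of week 2 with no prevalent injury, the apparent hazard ratio (low against high score) was 1.27 over 7 weeks and 1.13 over 16.

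**Step 4: a second model.** Cox regression on the continuous score, 1,200 cadets, 1,000 runs per scenario, 7-week window, CBT risk 10-30%, shift 0.25 to 1.0 SD:

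- end of week 1: hazard ratio per SD 0.96 to 0.85, false positives 7% to 87%;
- end of week 2: hazard ratio per SD 0.93 to 0.74, false positives 12% to 100%.

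The upper ends come from the 1.0 SD shift, which nothing in the documents supports or rules out.

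**Step 5: with the clock started at the questionnaire.** Removing cadets already injured, and prevalent cases where simulated, gave false-positive rates of about 4-6% in both models. The hazard ratio was about 1.00 (0.99 to 1.01 per SD in the Cox runs).

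**The case against.** A reader might infer that the plan does count injuries from before the score as predicted events. The documents do not go that far. Surveillance is Phase 2 and follows the questionnaire in Phase I; 10.1 calls the self-efficacy measure prospective; and the word for the starting default is not tied to a date. Phase 2 may be meant to start after the questionnaire, which would remove most of (a). The default may be no more than an opening code on the training-impact scale, and nothing says that it overrides the baseline answer. Nor does any text say that a flare of an old injury is coded as new. Section 9.6 also intends to study self-efficacy in combination with other risk factors, and 9.2 names prior injury as one.

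This stands as far as it goes: the fault is an undefined rule, not a specified error. It does not close the gap. The Phase 2 title and its tracking for the whole duration fit surveillance from the start of CBT equally well. Section 10.14 has injury information collected when the team is ready to analyse, so records could be drawn for the whole course. Even if record surveillance began at the questionnaire, the undated post-CBT self-report could still bring in a week-1 injury. An intention to look at other risk factors supplies no method, and adjusting for prior injury cannot repair (a), where the earlier injury is itself the counted outcome.

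Three further points on size stand. A session early in week 1 leaves almost nothing before the score, so the lower bound is 0%, not 14%. The highest rates in the table need the latest session date and the 7-week window. And 14.4 is conditional; it is not a planned conclusion that self-efficacy training prevents injury.

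**Conclusion.** The concern holds as a gap in the plan. The score is taken after CBT starts, all cadets begin as 'not injured' despite a baseline question on current injury, the outcome has no date condition, and the end of follow-up is not fixed. Injuries before the score (about 0-29% of CBT time) and injuries present at the questionnaire can therefore enter as predicted events, and may produce an association in the hypothesised direction.

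The size cannot be computed from the documents, which give no injury rate, score distribution or effect of injury on confidence. For score shifts of 0.25 to 0.5 SD on a median split, the illustrative false-positive rate is roughly 7% to 59% against a nominal 5%, and lower over 16 weeks than over 7 in most of the cells computed for both. That range should not be read as an estimate for this study.

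Only the observational Objectives 1 and 2 are touched; the randomised deadlift comparison is not. This is a cheap improvement.

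**What to change.** In 10.1 Phase 2 and 11.6 items 1-2:

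1. Start each cadet's injury clock on the date of the questionnaire. Count only injuries with onset after it, and treat cadets already injured in CBT as not at risk of a first event.
2. Set starting injury status from the baseline answer instead of the universal default. Handle cadets with a currently hindering injury either by leaving them out of the at-risk set or by stratification, and show the other as a sensitivity analysis. Either is acceptable if chosen in advance.
3. End the main analysis at the end of CBT, as the objectives state, and report the following weeks separately.
4. Add the date or week of injury onset to the post-CBT questionnaire.

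**Cost.** Wording in the protocol and analysis plan, plus one questionnaire item. The questionnaire date and baseline injury answer are already collected, and record entries can be expected to carry dates. Somewhat fewer injuries will count: under the assumptions of step 2, 16% to 32% of first CBT injuries fall before a form completed at the end of week 1 or 2, and fewer if the session is earlier.

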Cadet Demographics: Age, gender, height, weight, USMA Preparatory School attendance, intended athletics participation, intended USMA performance

Injury Questionnaire: Recent injury information (within last year), still effecting performance, and Single Assessment Numeric Evaluation (SANE), and after-cadet basic training injury presence, region, and limiting classification

Self-Efficacy: Overall Cadet Basic Training performance, marksmanship, buddy team live fire, swimming 150 yards, ruck marching (load carriage), ACFT, deadlift, land navigation

Maximum Deadlift (MDL) performance: Measured by the amount of weight successfully lifted during the ACFT.

Reported Self-Efficacy Source: Measured on the post-CBT survey using Qualtrics. The cadets will rank-order commonly cited sources of self-efficacy from most to least influential. The options will include commonly-cited self-efficacy sources: physiological state, previous experiences, affective state, mental imagery, vicarious experiences, and verbal persuasion.

10.3 At any point in the study, will you request, use, or access health information in any form, including

verbal, hard copy and electronic?

Yes No

10.4 Review the definitions below and respond to the following two questions. If you are not sure of the answers, email [contact] for assistance. The Military Health System (MHS) is defined as all DoD health plans and DoD health care providers that are organized under the management authority of, or in the case of covered individual providers, assigned to or employed by, the Defense Health Agency (DHA), the Army, the Navy, or the Air Force. MHS workforce members are employees, volunteers, trainees, and other persons whose conduct, in the performance of work for the MHS, is under the direct control of the MHS, whether or not they are paid by the MHS. MHS business associates are persons or entities that provide a service to the MHS and require protected health information (PHI) to provide the service.

Are you an MHS workforce member?

Yes, I am an MHS workforce member
 No, I am not an MHS workforce member

Are you an MHS business associate?

Yes, I am an MHS business associate
 No, I am not an MHS business associate

10.5 Have you consulted with an MHS data expert to determine the data elements required for your study?

Consulting with a data expert often saves time later in the compliance process because the data expert can advise on the data available in the numerous MHS information systems, the quality of that data and the methods for encrypting and collapsing data. To schedule a consult with an MHS data expert, send an email to: **([contact])**

Yes, then complete the questions below according to the data consult
 No, then complete the questions below according to the best of your knowledge

10.6 Indicate how you will request data from the MHS. Select all that apply.

Talking with MHS health care providers or MHS health plans about specific research participants

Obtaining MHS hard copy records specific to research participants
Obtaining data from an MHS information system(s)

10.7 If you are obtaining data from an MHS information system(s), indicate whether you plan to receive a data extract or whether you plan to access an MHS information system directly to create a data set.

A data extract is when the MHS or a contractor provides the data set directly to the researcher. When receiving a data set through data extract, the researcher may indicate whether the data elements should be provided as is, encrypted or collapsed. In contrast to a data extract, access to an information system means that the researcher may directly access an MHS information system and create a data set for the research study

Data Extract
 Access

10.8 Do you intend to request de-identified data from the MHS in your research study?

There are different two methods for de-identifying data pursuant to HIPAA:

1) Safe Harbor Method: Removing all of the identifiers listed in Table 1 below, provided that the researcher does not have actual knowledge that the remaining data can be used alone or in combination with other information to identify the individual who is the subject of the information

□ Statistical Method: An expert, with appropriate knowledge of and experience with generally accepted statistical and scientific principles and methods for rendering information not individually identifiable, determines that the data is not individually identifiable

Yes No

10.9 Indicate the MHS information system(s) from which you will seek to obtain data

If you do not know which system(s) contains the data elements you need, refer to the Guide for DoD Researchers on Using MHS Data or request guidance from an MHS data expert at: **DHA [contact]**.

Below is a list of commonly used MHS systems. If the system from which you seek to obtain data is not listed below, list the name of the system in the "Other MHS Systems" category below **PHI Systems:**

HS Information System	Requesting Data
AHLTA	 Yes
DMSS	 Yes
TMoosI	 Yes

PII -Only Systems:

HS Information System	Requesting Data
No records have been added	

De-Identified Data & Other Systems:

Information System	Requesting Data
Other MHS System (May include PII and/or PHI)	
List other system here:	 Yes
Cadet Illness and Injury Tracking System (CITTS)	

10.10 Do you intend to merge or otherwise associate the requested data with data from any sources outside of the MHS, including other DoD systems that are not part of the MHS?

Yes, will merge data
 No, will not merge data

10.11 Indicate the data elements about research participants or relatives, employers, or household members of the research participants that you will request from MHS hard copies or from MHS information systems.

If you will merge data, also indicate non-MHS data elements about research participants or relatives, employers, or household members of the research participants that you will have access to in any form or medium.

Data Element(s)	MHS	Non-MHS Systems	MHS Hard Copies
1. Names			

2. Postal address with only town, city, state and zip code			C
3. Postal address with all geographic subdivisions smaller than a state, including street address, city, county, precinct, zip code and their equivalent geocodes, except for the initial three digits of a zip code if, according to the current publicly available data from the Bureau of Census: 1) the geographic unit formed by combining all zip codes with the same three initial digits contains more than 20,000 people; and 2) the initial three digits of a zip code for all such geographic units containing 20,000 or fewer people is changed to 000			0
4. Dates including all elements (except year) directly related to an individual, including birth date, admission date, discharge date, and date of death	n	[J	-
5. Ages over 89 and all elements of dates (including year) indicative of such age, unless you will only request a single category of "age 90 or older"	0	0	Ci
6. Telephone numbers		l']	r
7. Fax numbers			

	n	n	r
8. Electronic mail addresses	n	rJ	r
9. Social Security numbers (SSNs)		n	r
10. Medical record numbers		0	r
11. Health plan beneficiary numbers	n	rJ	n
12. Account numbers	D	D	C
13. Certificate/license numbers	D	D	C
14. Vehicle identifiers and serial numbers, including license plate numbers	r1	r"J	r
15. Device identifiers and serial numbers		D	C
16. Web Universal Resource Locators (URLs)			D
17. Internet Protocol (IP) address numbers	D	D	C
¹⁰ 10.0: 1... LU. U1011lt;:Li 1... identifiers, including finger and voice prints		D	C
19. Full-face photographic images and any comparable images	n	D	r
20. Any other unique identifying number, characteristic, or code (Diagnosis,	n	0	r

DEERS ID, EDIPI,
Rank)

If you are obtaining SSNs, provide a justification as to why and explain why a substitute cannot be used

10.12 Do you believe it is possible for the MHS data to become identifiable because of triangulation, a small cell size, or any unique data element(s)?

Triangulation means using different data elements that are not themselves identifiable but that when combined can be used to identify an individual. For example, triangulation would use rank and race together to determine the identity of an individual with a particular health condition.

Small cell size means that there is only a small number of eligible individuals that satisfy the category description. Guidance for acceptable cell size is available from the Centers for Medicare and Medicaid Services. For example, the rank category of four star generals with a particular diagnosis may be less than 30, so the rank category may need to be expanded to include lower ranks.

A unique data element includes any unique features that are not explicitly enumerated in the categories of data in rows 1 - 20 of the table above (in Section 10.10), but that could be used to identify an individual. Unique data elements include characteristics that are not themselves identifying, such as the rank of general or admiral, or a race or gender, but within the context of other information could be identifiable.

Yes, I believe there is a reasonable possibility the MHS data will become identifiable
 No, I believe there is no reasonable possibility the MHS data will become identifiable

10.13 Have you completed and uploaded an appropriate HIPAA document (i.e. HIPAA Authorization will be obtained or Waiver/alteration of HIPAA Authorization is being requested)?

Yes
 No
 N/A

10.14 Managing Data (Data Management and/or Sharing Plan) and/or Human Biological Specimens for this Study:

Include in this section the plan for acquiring data (both electronic and hard copy), access during the study, data/specimen storage and length of time stored, shipment/transmission, and the plan for storage and final disposition at the conclusion of the study. Describe any data agreements in place for accessing data within and/or outside of your institution (e.g., Data Sharing Agreement, Data Use Agreement, Business Agreements, etc.)

The consent form, baseline questionnaire, CBT outcomes, and pre-ACFT / post-ACFT self-efficacy forms will all be hard copy acquired. The post-ACFT injury case report form will be electronically acquired through Qualtrics, a secure electronic survey application. All of the case report forms (hard copy and electronic) will require the participants name on them. No subject ID will be included on these forms to remain in compliance with human research protections guidelines. Once the hard copy case report forms are collected, the study data will be transcribed into an electronic spreadsheet where the participant will only be identified by their assigned subject ID. The only document (electronic or hard copy) linking the subject ID and the participant name will be the electronic master subject list. The hard copy case report forms with participant names on them will all be stored together in a folder with the participant's consent form. Participant folders will be stored together in a locked filing cabinet, behind locked doors, in a CAC card protected building. All electronic files will be stored on DoD-server, CAC card protected computers. Only the PI and AI's will have access to the physical and electronic participant files.

Performance information received from the Department of Military Instruction (DMI) is not considered private health information, but will include personnel identifiers. The information, to include copies of ACFT scorecards, will be collected from the DMI following the ACFT and stored

with the rest of the participants hard copy CRFs containing personnel identifiers. In addition, the researchers will collect outcomes data from the DMI (CBT and task-specific event performance outcomes data) via secure access to department databases and/or via encrypted emails or an encrypted drop box.

When we are ready for data analysis, we will subsequently collect injury information, number of days on profile for each subject for up to 9 weeks following cadet basic training. Subject number of days on profile will be combined with the previously de-identified study data on a spreadsheet for analysis. The spreadsheet data will be password and firewall-protected. There are no planned linkages with external databases, nor is transmission of the data for collaborative use anticipated. The PI will keep a master spreadsheet that links subject names with their unique identification number on a government computer assigned to the PI. The computer is password and CAC-card protected, and the system is firewall protected. This document will not be shown to anyone except for the investigators in this study or governmental agencies only in accordance with federal law. All research data and forms (both paper and electronic) will only be accessible by authorized study staff, the local IRB, and applicable governmental agencies as part of their duties and in accordance with federal law. These duties include making sure that research participants are protected.

10.15 Managing Data (Data Management and/or Sharing Plan) and/or Human Biological Specimens for Future Research:

If the study involves collecting, storing, or banking human specimens, data, or documents (either by the Investigator or through an established repository) for FUTURE research, address. How the specimens/data will be used, where and how data/specimens will be stored (including shipping procedures, storage plan, etc.), whether and how consent will be obtained, procedures that will fulfill subjects' request as stated in the consent, whether subjects may withdraw their data/specimens from storage, whether and how subjects may be recontacted for future research and given the option to decline, whether there will be genetic testing on the specimens, who will have access to the data/specimens, and the linkage, the length of time that data/specimens will be stored and conditions under which data/specimens will be destroyed.

All records containing HIPAA PHI will be maintained for a period of 6 years at which time they will be destroyed by securely shredding. The master list connecting unique study ID to participant identifiers will be destroyed upon study closure. De-identified research data will be maintained indefinitely.

Any data submitted to an approved agency for review will be linked only to the subject identification number and not the personal identity of the participant (ie, protected health information such as name, SSN, address, phone number, etc). If the data are used in scholarly presentations or journal articles, the investigators will protect the anonymity of individual patients and will report only aggregate data (e.g. group means) where appropriate. Participants will not be specifically identified in any publication or presentation of research results. No data sharing/use agreements are necessary or will be utilized.

